## 1.7 Specimen Collection as a Primary Source

N/A

## 1.8 Interviews, Focus Groups, Surveys, and/or Observations

### A. Administration

At the follow-up study visit, participants will complete a semi-structured interview with study staff to go over the previous week's sleep data. Specifically, study staff will download the sleep actigraph data and print out a summary of the actigraph-determined periods of sleep, rest, and wake as well as anytime the device was considered to be "off-wrist". Study staff will compare this data with sleep diary responses and call-in information. Any discrepancies will be reviewed with the participant and off-wrist periods will be confirmed or explained. Similarly, study staff will review wear the hip-worn device data to determine when the device was taken off, and reasons for being off. In addition, participants will complete a feasibility/acceptability questionnaire and then undergo a semi-structured interview with study staff to follow up on the responses in order to inquire about the participant's overall study experience and gain more information about sleep in adolescents to inform future studies. Study staff (study coordinator and research assistant) will be responsible for administering questionnaires and the PI will oversee all operations.

#### ▪ Timing and Frequency

Semi-structured interview regarding device data will occur at the follow-up visit, and is expected to last approximately 30-45 minutes.

Feasibility/acceptability questionnaire and follow-up interview will also occur during the follow-up visit and is expected to take approximately 10-15 minutes.

#### ▪ Location

A closed-door office space will be used to ensure participant confidentiality and privacy in Loree Classroom Building on Rutgers Cook/Douglass campus.

▪ **Procedures For Audio And Visual Recording**

N/A

▪ **Person Identifiers**

Subjects will be asked for their name and phone number for scheduling/recruitment purposes only. The study coordinator and PI will be the only research staff members that have access to person identifiers during the entire duration of the study. Participant person identifiers will be stored in a separate location from any study-related data. During the informed consent process, we will ask subjects and their parent(s) if they would like to be contacted in the future to be recruited for additional sleep studies. A separate section and checkbox will be included on the Parental Informed Consent form. Identifiable information will be stored in a separate database from the experimental data. Subject ID numbers will be assigned and used for data collection and analysis. For those who do not consent to be contacted in future studies, identifiers will be destroyed after completion of the study, or, in the event a participant does not continue with the study, after withdrawal from study participation.

## B. Study Instruments

Note: Study instruments will be converted to an online format using the Qualtrics survey platform. Supporting documents can be found in the eIRB submission

- **Anthropometrics:** At the orientation, participant's height (wall-mounted stadiometer, measured in duplicate) and weight (digital scale, measured in duplicate) will be measured using standard procedures (participant wearing street clothes, without shoes). These measures will be converted to BMIz and BMI percentile using age and sex-adjusted normative data from the CDC(18).
- **Demographic Questionnaire:** At the orientation, participants (with assistance of parents as necessary) will complete a demographic questionnaire which will include the following information: participant age, gender and racial and ethnic group, parent education and occupational status.
- **Child Chronotype Questionnaire:** At the orientation, participants will complete this questionnaire (7) in order to determine his/her chronotype. In adolescents, evidence suggests that chronotype, an individual's preference for activity early (morning-type, "lark") versus late (evening-type, "owl") in the day, affects sleep, diet and weight status (19, 20) which will be important information for planning the future metabolic health study.
- **Sleep Disorders Inventory for Students-Adolescents (SDIS-A):** At the orientation information obtained from this questionnaire (8) will determine if the adolescent is eligible for participation in the study. If a participant's score indicates that he/she may be at risk for a sleep disorder, the family will be referred to the Robert Wood Johnson Sleep Clinic, and the adolescent will not be eligible to participate in the study.
- **Mood questionnaire:** The Profile of Mood States Second Edition (POMS 2) instruments assess the mood states of individuals 13 years of age and older. The instrument is a self-report scale that allows for the quick assessment of transient, fluctuating feelings and enduring affect states(9).
- **Perceived Stress Scale:** The Perceived Stress Scale (PSS) measures the degree to which situations in one's life are considered stressful (10, 21). Previously, the PSS was designed for use in a population with at least a junior high school education. The questions are general in nature and easy to understand.

- **Freiburg Mindfulness Inventory:** The Freiburg Mindfulness Inventory (FMI) is a consistent and reliable scale used to measure mindfulness, and it has previously been validated for use in research and clinical applications to appropriately measure mindfulness(11, 22).
- **Actiwatch Spectrum Plus (Phillips Respironics, Murrysville, PA):** During the week between the orientation and follow-up visits, participants will wear the device on their non-dominant wrist across the 24-hour period. The device monitors motor activity to obtain continuous recordings of sleep-wake states (See Actiwatch and Accelerometer Information attachment for picture and spec sheet).
- **Sleep Diary:** During the week between the orientation and follow-up visits, participants will complete entries in a brief sleep diary daily. This provides a participant's estimate of bedtime and wake time, awakenings during the night, and daytime sleep (i.e. naps).
- **Actigraph GT3X (ActiGraph Corp, Pensacola, FL):** During the week between the orientation and follow-up visits, participants will wear the device (which is on a belt) on their right hip during waking hours. Motor activity is obtained in order to determine how much time the participant spends in sedentary, moderate and vigorous activity (See Actiwatch and Accelerometer Information attachment for picture and spec sheet).
- **Acceptability/Feasibility Questionnaire:** At the follow-up visit, participants will complete a brief questionnaire asking about their experience with the research study. Study staff will then conduct a semi-structured interview with the participant to follow-up on their responses.
- **Battery of Cognitive Tests via Joggle Research Application:** During the initial and follow-up visit a battery of cognitive tests will be administered to participants using Joggle, which is an iPad application(12). The first test is Motor Praxis Task (MPT), where boxes pop up in different places across the screen and will only disappear when tapped. Next is Visual Object Learning Task (VOLT), where participants are shown a set of shapes, and need to be able to recall the previous shapes when they are mixed in with new shapes. The NBACK test is a test where images are shown in a certain order and the participant needs to be able to pick an image that they had seen a certain number of screens before. Abstract Matching (AM) is a test where participants are shown a single shape, and 2 pairs of shapes, and needs to choose which pair fits the original shape. Line Orientation Test (LOT) is a test where participants need to rotate a line using the shortest path, so it will be parallel with another line. Digital Symbol Substitution Task is where participants are shown a list of numbers that correspond to symbols, and when they are shown a single symbol, they need to select the corresponding number. Balloon Analog Risk Task (BART) is a test where participants need to inflate the balloon on the screen to maximize the reward, but will receive nothing if the balloon pops. The last test is the Psychomotor Vigilance Test (PVT), participants are shown random stimuli and cannot respond early. The total battery will take approximately 20 minutes to complete and will be performed in a closed-door office space with minimal distraction. Trained research staff will be present to answer questions about the application.

## 2.2 Resources Available

### A. Facilities

Orientation and follow-up visits will be held at an office on the Cook/Douglass campus of Rutgers University. A closed-door office space will be used to screen participants for eligibility and describe study related procedures.

### B. Medical or Psychological Resources

Participants will be asked to complete a sleep disorders questionnaire. In the event a participant achieves a score that excludes them from the study, we will provide the participant with a referral to the Robert Wood Johnson Sleep Clinic.

### C. Research Staff Training

All members of the study staff will undergo mandatory clinical research IRB training as requested by Rutgers University. The study coordinator will be trained in informed consent/assent, protocol and research related procedures prior to the initiation of study-related tasks. Ongoing training will be administered to ensure that the study coordinator is competent in his/her duties and functions. Research assistants will be trained by the study coordinator and all trainings will be documented to ensure the appropriate trainings are delivered to staff persons working on study procedures.

## 3.0 Multi-Site Research Communication & Coordination

N/A

## 3.1 Non-Rutgers Site Research

N/A

## 4.0 Research Data Source/s

### 4.1 Primary Data: Subjects and Specimens

Primary data will be collected from subjects in this study. Subjects will consist of adolescents age 14-17y in the greater New Brunswick, NJ area.

## 4.2 Subject Selection and Enrollment Considerations

### A. Recruitment Details

Following IRB approval, subjects will be recruited from the greater New Brunswick, New Jersey area. Advertisements will be posted in the local community (e.g., at community centers, YMCAs, boys and girls clubs, libraries, high schools etc.) and on Rutgers University and Robert Wood Johnson Medical School campuses. We will seek approval from all locations before posting advertisements.

### B. Source of Subjects

Participants will be recruited from the greater New Brunswick, New Jersey area.

### **C. Method to Identify Potential Subjects**

Individuals will be screened for eligibility via a phone screen to minimize participant travel-burden to the study center. Upon arriving to the study center for the orientation visit, additional checks for eligibility (BMI, typical sleep and availability to complete the study) will be completed initially to avoid wasting the time of ineligible participants. Those that meet the inclusion/exclusion criteria and are considered eligible for the study will be provided with an overview of the study, the informed consent process, and asked if they would like to enroll. Enrollment will occur at the study orientation.

In accordance with the protocol modification Mod2018002469, subjects who were previously screened and determined ineligible based on weight status alone will be rescreened. Subjects who previously completed the phone screening questionnaire were asked if they would like to be contacted for future research studies. Only those who gave permission to be contacted will be contacted and rescreened.

### **D. Subject Screening**

A brief online screening questionnaire will be used for subjects who express interest in the research study. The online screening form will include the following topics: contact information, subject age, availability to complete the study, sleep habits.

After the study staff receives contact information from an interested individual, the individual will be contacted for a phone screen. The subject's parent will be asked to provide oral consent over the phone during the primary screening process to obtain confidential information related to eligibility and orientation scheduling. The parent will be read a statement of confidentiality (See Screening Script). A list of the items that will be covered in the screening interview will be read to the parent to ensure that the parent is aware of the screening process and the questions that are going to be asked of them. Study staff will ask the parent if they have questions or concerns prior to asking for oral permission and proceeding with screening-related questions. The study staff will ask the parent for permission to document identifiable information related to the subject's eligibility in the study. Verbal consent to the screening protocol will be documented on the Screening Script. The person obtaining oral consent will also sign and date this form. Initial eligibility will be determined using this screening tool and minimizes subject burden to the study location for the secondary screening and orientation. The phone screening script includes self-reported information including age, approximate weight and height of the child, availability to complete the study and current sleeping patterns.

Subjects who were previously screened for the research study will be screened again with an abbreviated screening form to capture transient data that may have changed from the initial screen (See Abbreviated Phone Screen). This abbreviated phone screen will include the following information: age, height and weight status, sleep habits, current enrollment in another research study and caffeine use. The research staff will provide the subject with both the study description and the confidentiality statement. Permission to document all variables will be obtained from the subject's parent.

Eligible individuals will be invited to the sleep center for an orientation. A secondary screening process will be needed to determine further eligibility (See Orientation Eligibility Form). We anticipate that a secondary screening process prior to the full written informed consent/assent process will minimize subject burden. Oral consent and assent from both the parent and child will be documented on a secondary screening document by the research coordinator/research assistant(s) to carry out procedures for additional checks for eligibility (measured BMI, typical sleep and availability to complete the study, complete the SDI-S questionnaire). These procedures are outlined in the Orientation Eligibility Form, which will be used to inform the parent and child about the orientation screening procedures. Study staff will ensure that the parent and child do not have any follow up questions or concerns. After oral consent and assent is obtained from both the parent and child, the research staff member who delivered this information will sign and date the form.

Following the additional screening procedures highlighted above, eligibility will be determined by the study staff based on inclusion/exclusion criteria. Eligible subjects will be asked to complete the written Parental Informed Consent Document and Assent of Participation in Research Activities Document before further research procedures can take place (See Consent section for further details on consent/assent process).

**■ Inclusion Criteria**

1. Parent-reported child age of 14-17 years
2. Typical sleep duration of approximately 7hr/night on school nights
3. BMI for age and gender in the >5th percentile but not greater than 100% overweight.
4. Parent must be the primary caretaker and at home during bed/wake times
5. Reported willingness and ability to complete all study-related tasks, including wearing the wrist actigraph and hip accelerometer daily.

**■ Exclusion Criteria**

1. Diagnosable sleep disorder (including Sleep Disordered Breathing) based on parent report and participant's score on Sleep Disorders Inventory for Students-Adolescents (SDIS-A).
2. Medication use or parent-reported diagnosis of a serious medical condition (including psychiatric conditions) that may impact sleep.
3. Excessive intake of caffeine (>300mg/day), drug (including nicotine) or alcohol use, or a history of substance abuse.
4. Actively trying to lose weight.
5. Transmeridian (east-west/west-east) travel during past month or planned travel during study time frame.
6. Inability to understand or complete protocol to ensure that consent/assent and reliable and valid measures are obtained.
7. Sibling of enrolled subjects, to minimize risk of bias in study findings.

**E. Recruitment Materials**

Printed flyers will be distributed across the Rutgers University campus. Additionally, we may reach out to local high schools, boys and girls clubs, libraries and YMCAs to advertise with printed flyers. Final versions of the print advertisements will be included for review, and we will seek posting approval from all locations prior to posting.

**F. Lead Site Recruitment Methods**

N/A

**4.3 Subject Randomization**

Condition assignments will be created by the PI and placed in sealed envelopes. Envelopes will be opened during the orientation visit by the study coordinator (there will be n=15 control and n=15 increase to 10h time-in-bed).

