**4.5 Number of Subjects**

**A. Total Number of Subjects**

We anticipate 30 total subjects to enroll in this pilot study.

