#### Document List:

- a. Parental Informed Consent Document
- b. Assent for Participation in Research Activities Document

On the consent form, we ask parents to indicate if they are willing to be contacted in future research studies. If a parent initials 'Yes, I agree to be contacted about future research studies,' we will provide them with a Contact Form which will include the name of parent, the name of the participant, the date as well as the preferred contact method. Parents and participants will be informed that in the event there is another research study they can participate in, the study staff will contact the family using the information provided on the Contact Form. The

Contact Form is the only document used to revisit families that documented interest in participation in additional research studies at Rutgers Sleep Lab.

▪ **Waiver of Documentation Of Consent**

N/A

▪ **Waiver or Alteration of Consent Process**

N/A

6.

7. **Consent Process**

▪ **Location of Consent Process**

The consent process will take place in Loree Classroom Building in a closed-door office space.

▪ **Roles for Individuals Involved in Consent**

The study coordinator will be responsible for obtaining written consent/assent at the initial orientation visit from both the parent and the child.

▪ **Coercion or Undue Influence**

The consent process is anticipated to take approximately 10-20 minutes, or as long as the participant needs to make an informed decision about participation in the study. All individuals involved in the informed consent/assent process will be educated that their participation in the research study is completely voluntary. Participants will be reminded that they have the ability to withdraw at any time and that their decision to participate will not have any impact on their availability of care. All study-related information will be clearly communicated and in writing in an organized fashion with understandable language. Exculpatory language will not be used in written consent or discussions about research.

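### Allocation concealment is weak: the PI writes the list to a fixed 15/15, and the coordinator who takes consent opens every envelope

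*Protocol*

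**What the plan says.** Section 4.3 of the protocol gives the whole allocation procedure in two sentences. The first is "Condition assignments will be created by the PI and placed in sealed envelopes". The second is that "Envelopes will be opened during the orientation visit by the study coordinator", with the totals in brackets: "there will be n=15 control and n=15 increase to 10h time-in-bed". Section 4.5 agrees on the sum: "We anticipate 30 total subjects to enroll in this pilot study". Section 1.3 is slightly looser and gives the extension arm as roughly 15.

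Other sections show who meets the families:

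- Section 4.6, on roles in the consent process: "The study coordinator will be responsible for obtaining written consent/assent at the initial orientation visit".
- Section 1.3: the phone screen is done by the coordinator or a research assistant.
- Section 4.2 D: study staff decide eligibility. The PI is not named there.
- The privacy provisions under Risks and Benefits: the coordinator handles scheduling and orientation.

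The inclusion criterion on sleep reads "Typical sleep duration of approximately 7hr/night on school nights". No range or tolerance is attached.

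The section heading and section 1.3 both describe the allocation as randomized. Nothing in the text shown says how the sequence is generated, whether the PI and coordinator are kept from seeing it, whether the envelopes are opaque or numbered, or whether each is opened only once eligibility is final.

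**The concern.** Sealed envelopes protect a comparison only if the people who admit families cannot foresee the next assignment. Here one person writes the list. A second person sees every result as it is opened, knows the final totals, takes consent, handles scheduling and may apply the entry criterion. Because that criterion is approximate, a borderline sleeper could be accepted, deferred or declined without breaking any written rule.

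Aim 1 compares the two arms on sleep obtained, and section 6.1 plans mixed-model ANOVAs between groups. The devices are issued at orientation for the intervention week only, so no actigraph baseline exists to show whether the arms started alike. With 15 per arm, a few selectively placed families could matter, and the result is meant to inform a larger study.

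**Working it through.** **The plan's own figure.** 15 + 15 = 30, which agrees with section 4.5. The protocol gives no power or sample-size calculation to reproduce (section 1.5), and this point needs none.

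**Assumptions.** The list is in random order within fixed totals of m = 15 per arm. The totals are kept. The guesser sees each opened envelope and always names the arm with more envelopes left.

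**Expected correct guesses over the trial** (Blackwell–Hodges):

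E = m + [4^m / C(2m, m) − 1] / 2

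- 4^15 = 1,073,741,824 and C(30, 15) = 155,117,520, so the ratio is 6.922.
- E = 15 + (6.922 − 1)/2 = 15 + 2.961 = 17.96.
- 17.96/30 = 59.9%, against 15/30 = 50% by chance.

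An exact recursion over the remaining counts gives the same 17.96.

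**Where the predictability sits.** With r envelopes left, let a be the number left in one arm (hypergeometric from 15/15). The chance of a correct guess is E[max(a, r − a)]/r. For the last five:

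| Envelopes left | Chance of a correct guess |
|---|---|
| 5 | 0.674 |
| 4 | 0.674 |
| 3 | 0.741 |
| 2 | 0.741 |
| 1 | 1.000 |

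The mean is 3.830/5 = 0.766, or about 77%. A simulation of 200,000 lists also gives about 77% for the last five, about 69% over the last ten and about 53% over the first ten. The weakness is concentrated late in recruitment.

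**Assignments known with certainty.** Once one arm is full, the rest are determined. The expected number is 2m/(m + 1) = 30/16 = 1.875.

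**The PI.** The author of a list who keeps its order could know up to 30 of 30. This is an inference from authorship. It would fail if the envelopes were shuffled after sealing, which the text neither states nor rules out.

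**Cost of dropping balance altogether.** Under simple 1:1 randomisation of 30:

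- P(15/15) = C(30, 15)/2^30 = 0.1445.
- P(14/16 or 16/14) = 2 × 0.1445 × 15/16 = 0.2709.
- P(arms differ by 0 or 2) = 0.1445 + 0.2709 = 0.415.
- P(arms differ by 4 or more) = 1 − 0.415 = 0.585, or about 58%.

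Simple randomisation brings guessing down to 15 of 30 but often leaves clearly unequal arms.

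**The case against.** The strongest case against is that this is a 30-person feasibility pilot with mostly descriptive analysis and no power calculation, that the allocation is called randomized and uses sealed envelopes, and that 60% is only modestly better than a coin. All of that is true, and it limits the importance of the point. It does not remove the point, because Aim 1 is explicitly comparative and the stated procedure is easily improved.

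Three stronger readings are tempting, and the documents do not support them.

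- **That assignment is not random.** A reader might infer this because no chance mechanism is named. The heading of section 4.3 and the wording of section 1.3 both say randomized. What is missing is the method and its separation from the study team.
- **That the PI can steer enrolment.** The phrase "the PI will oversee all operations" comes from section 1.8, on interviews and surveys, in a sentence about administering questionnaires. Where entry is described, the PI is not named as deciding it. The direct route is the coordinator. Sections 2.1 and 2.3 are listed in the contents but their text is not in the copy reviewed, so role details there cannot be checked.
- **That any imbalance in habitual sleep passes minute for minute into the Aim 1 estimate and cannot be corrected.** Everyone in the extension arm is prescribed 10 h in bed whatever their habit, so one-for-one transfer has no support for that arm. It is plausible only for controls, who keep their usual schedule. Typical sleep is also reported at the phone screen and again at orientation, so the arms can be compared on it and partly adjusted for it.

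The looser total in section 1.3 and the anticipated 30 in section 4.5 also mean that certainty about the last envelopes depends on 15/15 being kept.

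**Conclusion.** The point holds as a weakness in concealment. Under a random order with 15/15 kept, a coordinator who tracks the count would predict about 18 of 30 assignments (60%) and about 77% of the last five, with about 1.9 final assignments certain on average. The PI may know the order. Together with an approximate entry criterion applied by study staff, this leaves room for selection in a comparison without an actigraph baseline.

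The documents do not show that selection would occur, and they give no basis for sizing a bias in minutes of sleep. The figures measure opportunity only. In a small, mainly descriptive pilot this is a worthwhile and inexpensive improvement. It does not invalidate the study.

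**What to change.** Replace the first sentence of section 4.3 with:

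> The allocation sequence will be computer-generated by a colleague not involved in recruitment, consent or scoring, using a near-balanced list whose exact totals and block sizes are not disclosed to the PI or coordinator, and placed in sequentially numbered, opaque, sealed envelopes. Each envelope is signed and dated, and opened only after all eligibility checks (including the SDIS-A) and consent/assent are complete.

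The last clause is needed because section 1.3 places the SDIS-A check after enrolment, section 4.2 D places it before written consent, and neither says where the envelope falls. The bracketed n=15/n=15 in the second sentence should go as well, since it discloses the totals. Only telling staff that there will be about 15 per arm would add little, because section 1.3 already says nearly that for the extension arm.

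The cost is about an hour of a colleague's time, a wording change, and arms that may differ slightly from 15/15. A near-balanced list still lets a running count carry some information, so predictability falls but does not vanish. Unrestricted simple randomisation should not be used to remove the remainder, because about 58% of such lists would leave the arms differing by four or more.
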